15.4.2 Secondary Outcomes Measures

Effect on methamphetamine and other drug use during the 12-week treatment period

- **A.** Log weekly median quantitative methamphetamine level.
- **B.** The proportion of successful subjects with different patterns in the reduction in drug use examined as follows:
 - 1. Proportion of subjects with 3 consecutive weeks of abstinence as measured by 9 consecutive methamphetamine negative urine samples.
 - 2. Proportion of subjects who reduce the overall proportion of methamphetamine quantitative urine concentration to 50% or less of his/her baseline rate.
 - 3. Proportion of subjects who reduce the overall proportion of methamphetamine quantitative urine concentration to 25% or less of his/her baseline rate.
- **C.** Weekly mean proportion of methamphetamine non-use days based on subjects self report of use (SUR) during the 12-week treatment period.

- **D.** The maximum number of consecutive methamphetamine non-use days by subjects self report of use (SUR).
- **E.** The proportion of methamphetamine negative urines during the 12-week period.
- **F.** Weekly mean proportion of non-use days of other drug use, by other drug according to SUR.
- G. Proportion of negative urines or alcohol breathalyzer results for other drug use, by drug.

Reduction in the severity of methamphetamine dependence, craving, and withdrawal

- H. CGI-O scores.
- I. CGI-S scores.
- J. ASI-Lite scores.
- K. BSCS scores.
- L. MAWQ scores

Severity of Depression

M. HAM-D scores.

Changes in Cognitive Functions

N. Change in cognitive function at study end compared to baseline.

HIV Risk Taking Behaviors

O. Change in HRBS scores since baseline.

Treatment Retention

P. Number of days in treatment.

Safety of Bupropion

Q. AEs, laboratory data, physical exams, and vital signs.

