8.2 OUTCOME/RESPONSE MEASURES

The principal outcome measure is urine methamphetamine analysis. This outcome measure was selected as the primary study endpoint to examine the effect of treatment on an objective measure of reduction in methamphetamine use. However, as methamphetamine has an excretion half-life of 12 to 14 hours, carryover could result in a positive urine specimen even when the subject has not used. Therefore, this is potentially a conservative outcome measure of treatment effect.

Data from previous methamphetamine pharmacokinetic studies, as well as other outpatient studies, will be used to develop rules/algorithm for determining new versus old (carryover) use utilizing urine methamphetamine levels. As the urine samples in this study are being analyzed quantitatively for methamphetamine, if an algorithm is developed to determine new use versus carryover, this algorithm will be used for additional analyses.

Secondary outcome measures include:

- 1. Measuring reductions in drug use assessed by self-report of use;
- 2. Assessing the severity of methamphetamine dependence using the ASI-Lite and self and observer scored CGI;
- 3. Assessing changes in craving (determined BSCS);
- 4. Assessing the severity of withdrawal symptoms (determined by MAWQ),
- 5. Assessing changes in depression (determined by HAM-D score) and the association of these changes with reductions methamphetamine use;
- 6. Assessing the effect on the use days of other substances of abuse (opiates, marijuana, cigarette smoking, cocaine, and alcohol) as determined by self-report and negative urine (opiates, tetrahydrocannabinol, amphetamines, cocaine, benzodiazepines, or barbiturates) or alcohol breathalyzer results;
- 7. Assessing the effect on HIV risk taking behaviors;
- 8. Assessing the effect on cognitive functions; and
- 9. Safety of bupropion in the study population.

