13.2 BASELINE ASSESSMENTS

Baseline assessments to be completed over a 14-day consecutive period within the screening period include the following:

- 1. The following will be obtained three times a week for two weeks:
 - a. Alcohol breathalyzer test (a minimum of 4 breathalyzers must be collected in a consecutive 2-week period).
 - b. Urine toxicology screen using an onsite testing device. Subjects must provide at least 4 urine specimens in a consecutive 2-week period, at least one of which must be positive for urine methamphetamine (> 1000 ng/mL). Ideally, 3 of the specimens will be obtained in one week and 3 in the next week. No more than 4 of the specimens may be obtained in one week of the two-week baseline and no more than two specimens can be collected on consecutive days.
 - c. Urine methamphetamine plus creatinine measurements. Note: Methamphetamine assay will be performed only for the urine samples collected for the subjects who meet the eligibility criteria for the study.
 - d. MAWQ (a minimum of 4 MAWQs must be collected in a consecutive 2-week period).
- 2. The following must be obtained weekly for two weeks:
 - a. BSCS
 - b. CGI-S
 - c. CGI-O
 - d. Urine toxicology screen (urine specimen sent to NWT for analysis). This is only for subjects who are randomized on the study.
- 3. Daily report of methamphetamine, marijuana, nicotine, alcohol, opiates, and cocaine use will be recorded at each visit on a SUR eCRF.
- 4. HAM-D will be administered biweekly.

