13.6.14 Urine Collection and Analyses

Urine will be collected for four types of analyses as follows:

- 1. Methamphetamine/amphetamine, creatinine, tetrahydrocannabinol, cocaine, barbiturates, opiates, and benzodiazepines analysis performed at a central laboratory.
- 2. Urine Toxicology Screen performed with a qualitative onsite test device for methamphetamine, cocaine, tetrahydrocannabinol, amphetamines, barbiturates, opiates, benzodiazepines, phencyclidine, and tricyclics.
- 3. Medical Urinalysis performed at a central clinical laboratory.
- 4. Urine pregnancy test performed using an onsite test device.

Depending upon the assessment schedule, urine samples will be collected and aliquoted into the appropriate number of specimens. One specimen will be held frozen at the clinical site as a back-up. The others will be tested immediately or will be frozen as appropriate. Specimens will be collected and tested as follows:
Methamphetamine, Creatinine, Tetrahydrocannabinol, Cocaine, Amphetamines, Barbiturates, Opiates, and Benzodiazepines Analysis.

During the screening and baseline period of the study, urine will be collected 3 times per week (generally Monday, Wednesday, and Friday, barring holidays and schedule conflicts). Upon randomization, the urine samples collected from subjects during the screening/baseline period will then be sent to NWT. NWT will screen the 1st sample of the week for cocaine, tetrahydrocannabinol, methamphetamine/amphetamines, barbiturates, opiates, benzodiazepines and creatinine. NWT will screen the 2nd and 3rd samples of the week for amphetamines/ methamphetamine and creatinine only, and NWT will do quantitative analysis for methamphetamine and amphetamines for all the samples screened positive by NWT for methamphetamine/amphetamines.

Note: The sites will store samples from screening until the subject is randomized, and once randomized then samples can be sent to NWT for analysis.

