Following randomization, during the treatment phase of the study and at each of the follow-up visits, urine will be collected 3 times per week (generally Monday, Wednesday, and Friday, barring holidays and schedule conflicts) and NWT will screen the first sample collected each week for cocaine, methamphetamine/amphetamines, tetrahydrocannabinol, barbiturates, opiates, and benzodiazepines. NWT will screen all samples for amphetamines/methamphetamine and quantitative creatinine, and NWT will quantitate amphetamines and methamphetamine for all samples, which screen positive by NWT for methamphetamine/amphetamines.

All specimens collected during this time frame and screened positive by NWT for methamphetamine/amphetamines will be subjected to methamphetamine quantitative analysis performed at NWT for the determination of "new use." The back-up sample retained at the site will be stored frozen until the NIDA data-coordinating center has notified the site that it can be disposed.

Urine Toxicology Screen Using an Onsite Testing Device. During the screening and baseline period, urine will be collected 3 times per week (generally Monday, Wednesday, and Friday, barring holidays and schedule conflicts). After the backup aliquot and central laboratory testing aliquot has been taken, these samples will be analyzed using an on-site testing device (tetrahydrocannabinol, methamphetamine, cocaine, amphetamines, barbiturates, opiates, benzodiazepines, tricyclics, and phencyclidine). Samples positive for amphetamine (the onsite testing device has a cutoff of greater than or equal to 1000 ng/mL) will be considered as positive for methamphetamine for inclusion criteria purposes.

During treatment and after the backup aliquot and central laboratory testing aliquot has been taken, the first urine sample collected each week will be analyzed using an on-site testing device.

A frozen aliquot of every sample will be stored at the site. At treatment termination and followup, samples will be sent to a central lab for analysis, be subjected to onsite testing, and an aliquot will be frozen on site as back up. Results of on-site testing will be provided to the clinical staff as well as the investigative staff for the safety of the subjects.

Medical Urinalysis. Urine will be collected and analyzed for specific gravity, pH, blood, protein, glucose, ketones, leukocytes, and nitrites. The analysis will be conducted at a central clinical laboratory.

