15.4 OUTCOME MEASURES

15.4.1 Primary Outcome Measure

The primary outcome variable for each subject is the weekly proportion of methamphetamine– free urine samples. Three urine collection days are scheduled per calendar week. The weekly methamphetamine-free sample is recorded as "0" if all three urine samples in the week were less than 300 ng/ml. The weekly methamphetamine-free sample is recorded as "1" if the proportion of weekly methamphetamine-free samples is between 0.67 and 0.75, inclusive. The weekly methamphetamine-free sample is recorded as '2' if the proportion of weekly methamphetaminefree samples is between 0.33 and 0.5, inclusive. The weekly methamphetaminefree samples is between 0.33 and 0.5, inclusive. The weekly methamphetamine-free sample is recorded as "3" if the proportion of weekly methamphetamine-free samples is 0.

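### Secondary measures A, B2 and B3 rest on urine concentration without the creatinine correction that the collected data allow, and B2 and B3 cannot be computed unambiguously as worded

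*Protocol*

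**What the plan says.** Section 15.4.2 of the protocol sets three secondary outcomes on the quantitative urine result:

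- Measure A: "Log weekly median quantitative methamphetamine level".
- Measure B2: "Proportion of subjects who reduce the overall proportion of methamphetamine quantitative urine concentration to 50% or less of his/her baseline rate".
- Measure B3: "Proportion of subjects who reduce the overall proportion of methamphetamine quantitative urine concentration to 25% or less of his/her baseline rate".

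Section 15.6.1 analyses A by GEE and B by chi-square tests. Neither analysis has a creatinine term.

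Creatinine is nevertheless available throughout. For baseline samples, section 13.6.14 includes it in the panel for the first sample of each week and adds that "NWT will screen the 2nd and 3rd samples of the week for amphetamines/ methamphetamine and creatinine only". After randomization, "NWT will screen all samples for amphetamines/methamphetamine and quantitative creatinine". Sections 13.2 to 13.5 list it beside methamphetamine at baseline, on treatment, at termination and at follow-up. Section 15 does not mention it.

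Section 16.3 says the statistical analysis follows the protocol's own analytical plan, that is, section 15. The new-use algorithm foreseen in sections 8.2 and 15.9 names urine levels and self-report, not creatinine, and is meant for additional or post hoc work.

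**The concern.** There are two linked problems.

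**Scale.** A spot urine concentration reflects how dilute the urine is as well as how much drug was excreted. Section 8.2 states that "methamphetamine has an excretion half-life of 12 to 14 hours", so a twofold dilution lowers the reading as much as one half-life without use. The information needed to separate the two is collected and then left out of the outcomes.

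**Wording.** B2 and B3 speak of an overall proportion of a concentration, compared with a baseline rate. A proportion or rate is a share of samples; a concentration is in ng/mL. The text does not say which is to be compared with baseline, and the two can classify the same subject differently.

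The stake is the usefulness of these outcomes. Section 15.3 says the objectives should help to define a clinically meaningful response, and section 15.7 says the trial should guide the design and power of a later study. Avoidable noise and a responder definition with two readings weaken both uses.

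**Working it through.** The protocol gives no power or sample size for these outcomes (section 15.7 says none could be calculated), so there is no stated figure to reproduce.

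**1. The two readings of B2 and B3.** This step needs no assumption. Take a subject whose urines are all positive at baseline and on treatment, with concentration falling to one fifth.

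- Proportion reading: ratio to baseline 1.00, so a non-responder on both.
- Concentration reading: ratio 0.20, so a responder on both (0.20 ≤ 0.50 and 0.20 ≤ 0.25).

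**2. What dilution does.** Concentration = amount / volume. With unchanged use and k-fold dilution relative to baseline, the ratio is 1/k: k = 2 gives 0.50 (meets B2) and k = 4 gives 0.25 (meets B3). Dividing by creatinine removes k, because (M/k)/(C/k) = M/C.

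If only a fraction f of treatment samples is diluted k-fold, the mean reaches a threshold c when f = (1 − c)/(1 − 1/k):

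- c = 0.50: k = 3 needs 75% of samples, k = 4 needs 67%, k = 10 needs 56%.
- c = 0.25: k = 4 needs 100%, k = 10 needs 83%.

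Dilution must therefore be sustained to produce a response by this route.

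**3. Chance dilution at subject level.** Inputs from the protocol:

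- Baseline (section 13.2): "Subjects must provide at least 4 urine specimens in a consecutive 2-week period", ideally 6.
- Treatment (section 15.4.1): "Three urine collection days are scheduled per calendar week", so 3 × 12 = 36.
- Evaluable minimum (section 15.5): 6 on-study samples.

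Assumption, not in the documents: SD of ln(creatinine) between samples s = 0.5 to 0.8, with lognormal, independent dilution and unchanged use.

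Comparing log means, P = Φ( ln c / (s·√(1/n_b + 1/n_t)) ), where n_b and n_t are the numbers of baseline and treatment samples.

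- 6 and 36 samples, √(1/6 + 1/36) = 0.441. B2: ln 0.5/(0.5 × 0.441) = −3.14, P = 0.08%; ln 0.5/(0.8 × 0.441) = −1.96, P = 2.5%.
- 4 and 6 samples, √(1/4 + 1/6) = 0.645. B2: −2.15, P = 1.6%; −1.34, P = 9.0%. B3 at s = 0.8: ln 0.25/(0.8 × 0.645) = −2.68, P = 0.4%.

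The protocol does not say how samples are summarised. Simulating the same model with arithmetic means or medians gives:

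| Baseline / treatment samples | False B2 responders | False B3 responders |
|---|---|---|
| 6 / 36 | about 0.1% to 5% | below 0.1% |
| 4 / 6 | about 2% to 12% | at most about 1% |

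**4. How much the correction gains.** Assume further that the SD of ln(methamphetamine) is 1.5 to 2.0 and treat it as within-subject. Compare log means with 4 and 36 samples, √(1/4 + 1/36) = 0.527, and no change in average use.

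- SD 1.5, uncorrected: Φ(−0.693/(1.5 × 0.527)) = 19.0%. Removing dilution variance leaves SD √(2.25 − 0.25) = 1.41 or √(2.25 − 0.64) = 1.27, giving 17.6% or 15.0%.
- SD 2.0, uncorrected: 25.5%. After removal: 24.9% or 23.7%.

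The gain is 0.7 to 4.0 percentage points.

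**5. Measure A.** A weekly median rests on about three samples, so it averages out little. Under the same SDs, taken to apply to positive samples, dilution supplies between 0.25/4.0 = 6% and 0.64/2.25 = 28% of the sample-level variance.

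**The case against.** **A SAP that is not shown may normalise the values, and the protocol never says raw.** It pairs methamphetamine with creatinine in the assessment schedule, and section 15.6.1 allows adjustments. This stands in part: nothing rules creatinine out. But section 16.3 makes section 15 the governing plan, and section 15 names a level and a concentration. The wording conflict in B2 and B3 is there in any case.

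**The effect is small.** This largely stands. A reader might compare one sample with one other, where Φ(ln c/(s√2)) gives 16% to 27% at the 50% threshold and 2% to 11% at 25%, and take these as rates of false response. They are not: B2 and B3 set an overall level against at least 4 baseline samples, and the subject-level rates are far lower. Day-to-day variation in use dominates, so the correction gains only a few percentage points. Few-sample subjects are still realistic: section 15.7 reports 46% to 50% dropout, and the intent-to-treat population has no minimum number of urines.

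**There is no bias.** This stands. A reader might infer that the comparison of arms is distorted. The trial is randomised and double-blind, and the documents give no reason to expect dilution to differ by arm.

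**The same argument would reach the primary outcome.** Dilution can move a sample below 300 ng/mL, but twofold dilution does so only for samples between 300 and 600 ng/mL, whereas it shifts every value on a concentration scale. The point does not extend to the primary rule.

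**A ratio needs a numerator.** This stands. Section 13.6.14 quantifies only samples that screen positive, so a rule for negatives is required.

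**Conclusion.** The point holds for three secondary outcomes. That B2 and B3 have two incompatible readings, and that creatinine is collected but unused in section 15, follows from the text alone. The size of the dilution effect rests on the assumed SD of ln(creatinine) of 0.5 to 0.8 and on independent dilution. With unchanged use, about 0.1% to 5% of subjects become B2 responders by chance dilution with full sampling and 2% to 12% near the minimum; for B3 the share is at most about 1%. Beyond chance, meeting B3 with unchanged use needs sustained dilution of about fourfold or more, and no passage suggests that this occurs. The consequence is avoidable noise and some misclassification. The change is worth making because it is cheap and settles the definition; the expected gain in precision is modest.

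**What to change.** - **Measure A:** define it as the log of the weekly median methamphetamine/creatinine ratio.
- **B2 and B3:** define a responder as a subject whose average (or median; choose one) on-treatment ratio is 50% or less, or 25% or less, of the same summary at baseline. Delete *overall proportion of* and *rate*.
- **Screen-negative samples:** state one fixed value on the ratio scale, so that negatives do not vary with creatinine and the logarithm is defined.
- **Sensitivity analysis:** report the three measures on raw concentration.

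The cost is endpoint wording, one derived variable and one substitution rule; no new data are needed. One small drawback is that creatinine output differs between people. B2 and B3 compare each subject with his or her own baseline, and randomisation balances this in expectation for A. The primary outcome, alpha and sample size stay as they are.

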15.5 INTENT-TO-TREAT AND EVALUABLE SUBJECT POPULATIONS

The intent-to-treat population is defined as subjects who were randomized and received at least 1 dose of study agent. The evaluable population is defined as the subjects who are eligible to

participate in the study in accordance with the inclusion and exclusion criteria and who contribute at least six (6) usable on-study urine samples and 28 days of self-report of substance use.

15.6 ANALYSIS PLAN

15.6.1 Efficacy Assessments

Each of the primary and secondary efficacy outcome measures will be analyzed for the intent-totreat and for the evaluable population. Major differences in the results, if any, will be further explored. While there is every intent to be complete in describing the analyses to be performed, it is not possible to anticipate every contingency and some adjustments may be required to meet constraints posed by the structure of the data.

Statistical tests will be two-sided at a 5% Type I error rate. Confidence intervals will be two-sided with a 95% confidence coefficient.

Primary Efficacy Outcomes

The weekly mean proportion of methamphetamine-free urines on study will be compared between treatment groups using Generalized Estimating Equations (GEE) for ordinal categorical response (Lipsitz *et al.*, 1994). GEE provide a model-based regression method applicable for the analysis of the correlated data that will result from this repeated measures longitudinal study. The GEE procedure was first proposed by Liang and Zeger (1986) and Zeger and Liang (1986) and models the population average. GEE has several useful features:

- 1. It can be used to analyze different types of outcomes such as continuous, binary, or count.
- 2. It can be used to analyze an unbalanced design caused by either differing numbers of observations per person or by observations taken at different times.
- 3. The parameter estimates are consistent even if assumptions about the variance structure are not completely accurate.

As a secondary analysis, the individual effects, if any, of age, race, site, and usual route of methamphetamine use (oral/nasal inhalation versus intravenous/smoked) on the primary treatment effects will be determined where numbers permit. The first order interactions of these variables with gender, historical self-report of methamphetamine use (prior use in the last 30 days ≤ 18 versus > 18), and severity of depression (HAM-D score ≤ 12 versus >12) will also be included in the model. Presentation will include the full model with all terms and a reduced model containing only significant terms.

Secondary Efficacy Outcomes

Unless the primary response analysis implies the need for a more elaborate model, between group comparisons of the secondary outcomes will be performed as follows:

- 1. Log weekly median quantitative methamphetamine, weekly mean proportion of methamphetamine non-use days by self-report, weekly mean proportion of non-use day of other drug use, measures A, C, and F, will be assessed by GEE.
- 2. Proportion of successful subjects and negative urines for other drugs or alcohol breathalyzer tests, measures B and G, will be assessed by Chi-square tests.
- 3. The maximum number of consecutive methamphetamine non-use days, proportion of methamphetamine negative urines, change in cognitive function, and change in HRBS scores at termination compared to baseline measures D, E, N, and O will be assessed by t-test.
- 4. Repeated measures of CGI-S, CGI-O, BSCS, ASI-Lite, MAWQ, and HAM-D scores, measures H, I, J, K, L, and M will be assessed by GEE.
- 5. Survival analysis will be performed on retention data (measure P). The Wilcoxon (Gehan) test will be used to test the hypothesis that the survival distribution of the bupropion group will be the same as those of the placebo group.
- 6. Adverse events, laboratory data, physical exams, and vital signs will be reported in tabular form. AEs will be listed indicating the frequency of each type of event by various demographic characteristics such as gender, ethnicity, age, duration of addiction, other medical problems both related to and independent of the addiction, and combinations of these characteristics. The frequencies of adverse events by type will be compared between study arms using Chi-square analyses.

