8.4 RANDOMIZATION PLAN

Adaptive random allocation of subjects to study groups was developed to balance groups with respect to screening prognostic variables. The procedure allocates treatment assignment based on the assignments and prognostic variable levels for all previously enrolled subjects. The treatment groups will be balanced with respect to gender, historical self-report of methamphetamine use (prior use in the last 30 days ≤ 18 *versus* > 18), and severity of depression (HAM-D score ≤ 12 *versus* >12). A new subject will be randomized with a "biased coin" procedure, which uses randomization probabilities, favoring the treatment with the deficit enrollment, to improve the balance on group assignment. The randomization process will be performed by KAI.

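### The primary GEE names none of the three factors used to balance allocation and ignores the baseline urines: precision is given up, and the test is conservative to an unknown, possibly negligible, degree

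*Protocol*

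**What the plan says.** Section 8.4 gives the purpose of the allocation scheme: "Adaptive random allocation of subjects to study groups was developed to balance groups with respect to screening prognostic variables". It then names the factors: "The treatment groups will be balanced with respect to gender, historical self-report of methamphetamine use" (split at 18 days in the last 30), and depression severity (HAM-D split at 12). The mechanism is a biased coin, "which uses randomization probabilities, favoring the treatment with the deficit enrollment, to improve the balance on group assignment"; the coin probability is not stated.

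Section 15.6.1 describes the primary analysis: "The weekly mean proportion of methamphetamine-free urines on study will be compared between treatment groups using Generalized Estimating Equations (GEE", in the form for an ordinal outcome. No covariate is listed. Covariates come in the next step: "As a secondary analysis, the individual effects, if any, of age, race, site, and usual route of methamphetamine use" are to be examined where numbers permit. The balancing factors are named only after that: "The first order interactions of these variables with gender, historical self-report of methamphetamine use" and HAM-D severity join that secondary model, which is presented in full and again with only its significant terms.

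Baseline urine data will exist for every randomised subject. Section 13.2 requires at least four specimens over two weeks, ideally six, with at least one positive. Section 13.6.14 adds: "Upon randomization, the urine samples collected from subjects during the screening/baseline period will then be sent to NWT", the laboratory that also tests the on-study samples. Section 15.6.1 gives these results no role in the primary model.

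Section 15.9 lists depression and baseline use patterns as subjects for possible post hoc work. Section 16.3 says the statistical analysis follows the protocol's own analytical plan section.

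**The concern.** Balancing allocation on a prognostic factor removes part of the chance variation in the treatment difference. A model that omits the factor still counts that variation in its standard error. The standard error is then too large, the true type I error falls below 5%, and power is lost. The design would pay for balance, and the analysis would not collect the benefit.

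The baseline urine result works differently. It is not a balancing factor, so a chance imbalance in it is honestly reflected in the unadjusted standard error. Leaving it out does not distort the test. But it is the same kind of measurement as the outcome, from the same laboratory, and probably predicts the outcome better than gender or two dichotomised scores.

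Precision matters here. Section 15.7 reports that no sample size could be calculated and that dropout was 46%-50%. Enrolment was raised from 100 to 150 to gain information.

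**Working it through.** **The plan's own figure.** There is none to reproduce: section 15.7 gives 150 subjects with no effect size or variance. For scale only, a simple comparison of 75 per arm at two-sided 5% and 80% power detects a standardised difference of (1.960 + 0.842) × √(2/75) = 0.46, ignoring repeated measures and dropout.

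**Inputs.** From the documents: two-sided alpha 0.05 (15.6.1), 150 subjects and 46%-50% dropout (15.7), three balancing factors (8.4). Assumed: R², the share of between-subject outcome variance that the three factors explain. The documents give no value, so a range is shown.

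**Formula.** Let s be the standard error that the unadjusted model reports. Under close balance the estimate's true standard deviation is s√(1−R²), so the test rejects only when the correctly scaled statistic exceeds c = 1.960/√(1−R²).

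- Actual level = 2 × [1 − Φ(c)].
- Power, for an effect with 80% power when adjusted = 1 − Φ(c − 2.802).

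| R² | c | Actual level | Power unadjusted (80% adjusted) |
|---|---|---|---|
| 2% | 1.980 | 0.048 | about 79% |
| 5% | 2.011 | 0.044 | about 79% |
| 10% | 2.066 | 0.039 | 77% |
| 20% | 2.191 | 0.028 | 73% |
| 25% | 2.263 | 0.024 | 70% |

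**Simulation of the design.** 150 subjects; a biased coin of 0.8 (assumed) on the three factors; twelve weekly four-level scores; 48% dropout; cumulative-logit GEE with working independence and sandwich standard errors; 1,500 null and 600 alternative runs per scenario. Factor strengths and the treatment effect are assumptions. Each cell reads: unadjusted / three factors / three factors plus baseline urine.

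| Factors | Type I error | Power |
|---|---|---|
| weak | 0.046 / 0.055 / 0.061 | 0.91 / 0.90 / 1.00 |
| moderate | 0.057 / 0.069 / 0.065 | 0.88 / 0.89 / 1.00 |
| strong | 0.032 / 0.057 / 0.060 | 0.80 / 0.90 / 1.00 |

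The Monte Carlo standard error of the type I figures is about 0.006.

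- With strong factors the mean reported standard error was 0.239 and the true standard deviation 0.214. The ratio (0.214/0.239)² = 0.80 implies R² of about 20%, where the formula gives 0.028; the simulation gave 0.032. Under simple randomisation the same unadjusted test ran at 0.053 (600 runs), so the balancing causes the conservatism.
- With weak or moderate factors no conservatism was detectable, and adjusting for the three factors alone did not change power detectably.
- Adding baseline urine lowered the standard deviation of the treatment estimate under the null from 0.221 to 0.188 (weak) and from 0.224 to 0.193 (moderate). That is 1 − (0.188/0.221)² = 28% and 1 − (0.193/0.224)² = 26% of the variance. The simulation tied baseline urine to the on-study outcome by construction and did not impose the entry rule of at least one positive, so this shows direction rather than a forecast.

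**The case against.** The strongest reply is that the protocol never calls the primary comparison unadjusted. It calls GEE a regression method, and covariate lists are commonly left to an SAP, which is not at hand here. Interaction terms also normally presuppose main effects, so the balancing factors could be meant to sit in the base model. This stands in part: a reader who infers that the protocol forbids adjustment goes too far. But the protocol does more than stay silent. It places covariates in a secondary analysis, mentions depression and baseline use patterns again as post hoc topics, and refers the analyst back to this section.

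A reader might also infer that the primary test is materially conservative. The documents do not support that. They call the factors prognostic but give no strength, and the coin probability that determines how close the balance will be is missing. At R² of 2% to 5% the level is 0.048 to 0.044.

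A third tempting step is to value the baseline urine in subjects. With an assumed correlation of 0.5, the linear-model rule gives 150/(1 − 0.25) = 200. That rule does not carry over directly to an ordinal GEE, where adjustment on the logit scale changes a marginal effect into a conditional one. The correlation has no source in the documents, and the required positive specimen keeps the baseline proportion of clean urines below 1.

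Adjustment is not free either. The adjusted sandwich tests ran at 0.055 to 0.069 in simulation. Site is not a balancing factor, and the protocol examines it only where numbers permit. These objections limit the remedy and do not remove the point.

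**Conclusion.** The point holds as a should-fix matter of efficiency. It alleges no bias and no excess of false positives in the primary comparison.

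Two separate losses should not be merged. Omitting the three balancing factors can lower the actual level, from about 0.048 at R² of 2% to about 0.024 at 25%, with power falling from 80% to about 70% at the upper end. This rests on close balance and an assumed R²; with weak factors the loss is negligible. Omitting the baseline urine result leaves type I error alone, apart from whatever it shares with the prior-use factor already counted above, and costs precision and power. It is probably the larger loss, but its size cannot be derived from the documents.

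**What to change.** State in section 15.6.1, before unblinding:

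- The primary GEE contains treatment, week, main effects of gender, prior use (≤18 versus >18 days) and HAM-D (≤12 versus >12), and the baseline proportion of methamphetamine-free urines. The treatment coefficient is the primary test.
- The sandwich variance carries a named small-sample correction.
- The adjusted odds ratio is conditional on the covariates; the unadjusted estimate is reported beside it.
- Site and the interactions stay in the secondary analysis.

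The data are already collected under the protocol. The cost is a short amendment, slightly more analysis work, and a conditional rather than a marginal effect as the primary estimate. Fixing the list before unblinding keeps covariate choice from depending on the results.
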